## Evaluation Schedule

Evaluation	Preop	Peri-op	6 weeks ( $\pm$ 2 wks)	3 months ( $\pm$ 1 mo)	6 months ( $\pm$ 1 mo)	1 year ( $\pm$ 2 mos)	2 years ( $\pm$ 2 mos)
Inclusion/ Exclusion	X						
Demographics & Medical History	X						
Preoperative Functional Evaluation	X						
Surgical Details		X					
SF-12	X		X	X	X	X	X
Post- operative Functional Evaluation			X	X	X	X	X
VAS (back and leg)	X		X	X	X	X	X
ODI	X		X	X	X	X	X
AP/Lateral	X		X	X	X	X	X
Flexion/Extension	X					X	X
Long standing Lateral	X					X	
MRI	X						
CT (fusion analysis)						X	X*

\* Month 24 CTs are only expected for subjects that did not have a successful fusion at Month 12. All Month 24 CT collected will be analyzed.

CONFIDENTIAL

This material is the property of Stryker Spine. Do not disclose or use except as authorized in writing by Stryker.  
 Page 13

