## Study Synopsis

Title	A Prospective Multi-Center Evaluation of a hydraulic expandable TLIF cage for the treatment of Degenerative Disc Disease of the Lumbar Spine
Short Title	APROPOS (AccuLIF® Prospective Patient Outcomes Study)
Protocol Number	2015-L-001
Phase	Post-Market
Methodology	This is a prospective, post-market, multi-center, clinical evaluation of the AccuLIF expandable TLIF cage in patients requiring arthrodesis for degenerative disc disease (DDD) or DDD with up to Grade I spondylolisthesis or retrolisthesis at one or two contiguous levels between L2 and S1. DDD is defined as back pain of discogenic origin with degeneration of the disc confirmed by history and radiographic studies.
Study Duration	Enrollment period: approximately 9 months Study follow-up period: each subject will be followed for 24 months (2 years) Total study duration: approximately 36 months
Study Center(s)	Up to 10 centers in the US will participate
Hypothesis	
It is hypothesized that patients implanted with the AccuLIF expandable TLIF cage will show restoration of anterior, middle, and posterior disc height, improve segmental lordosis and maintain regional and global sagittal balance post operatively.
 
Primary success is defined as an increase of 3 degrees or more of segmental lordosis post operatively.
 
It is also hypothesized that patients implanted with the AccuLIF expandable TLIF cage will show improvement in post-operative clinical outcomes when compared to pre-operative clinical status.

CONFIDENTIAL

This material is the property of Stryker Spine. Do not disclose or use except as authorized in writing by Stryker.  
Page 7

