This material is the property of Stryker Spine. Do not disclose or use except as authorized in writing by Stryker.  
Page 11

Ancillary Devices	
The AccuLIF system is indicated for use with autogenous bone and/or allograft (cancellous or corticocancellous allograft chips) and supplemental fixation. Stryker supplementation fixation (Xia or ES2 pedicle screws must be used as part of the study protocol).

Statistical Methodology	
All continuous data will be summarized using continuous descriptive statistics: number of subjects with responses (n), mean, standard deviation, median, minimum, and maximum. Changes from baseline, where appropriate, will be calculated as the follow-up measure minus the baseline measure, where baseline is defined as the last measure prior to the AccuLIF spinal system surgical procedure.
 
All categorical data will be summarized using counts and percentages. Denominators for percentages will be the number of subjects in the respective patient population with nonmissing data.
 
For the primary endpoint of an increase of 3 degrees or more of segmental lordosis, a one-sided analysis (<math>\alpha=0.05</math>) will be used to assess significance. A one-sample t-test will be employed. Although the primary analysis will be at 24 months, similar analyses will be performed at each visit. Both the change from baseline and the results at each visit will be summarized.
 
For all other radiographic parameters, the change from baseline will be analyzed at each visit using two-sided, one-sample t-tests (<math>\alpha=0.05</math>) comparing the change from baseline to 0.
 
Secondary and exploratory endpoints will be analyzed where appropriate. Where changes from baseline can be calculated for numerical data, statistical analyses will be performed. Analyses will follow the two-sided approach taken for the primary analyses. Data that is ordinal in nature, such as the changes in clinical outcomes, may be analyzed using Wilcoxon signed rank tests, comparing baseline measures to follow-up measures. All analyses will be two-sided and evaluated at an alpha level of 0.05.

CONFIDENTIAL

This material is the property of Stryker Spine. Do not disclose or use except as authorized in writing by Stryker.  
Page 12

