## **7.6 12 Month Visit**

During the 12 month visit (365 days after surgery  $\pm$  8 weeks, study days 309 – 421), SF-12, VAS (back and leg), ODI and patient satisfaction will be collected; neurological status (reflex, sensory, motor); subject's current pain medication, work status, and smoking status will be

CONFIDENTIAL

This material is the property of Stryker Spine. Do not disclose or use except as authorized in writing by Stryker.  
Page 21

assessed. AP/Lateral and Flexion/Extension radiographs, and long standing lateral will be taken. CT scan to assess bony fusion, will be taken as well.

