## 7.7 24 Month Visit

During the 24 month visit 24 months (730 days after surgery  $\pm$  8 weeks, study days 674 – 786), SF-12, VAS (back and leg), ODI and patient satisfaction will be collected; neurological status (reflex, sensory, motor); subject's current pain medication, work status, and smoking status will be assessed. AP/Lateral and Flexion/Extension radiographs will be taken. For subjects that did not have a successful fusion at Month 12, a 24 month CT scan will be taken to re-assess fusion.

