#### 9.1.4 Secondary Objective Parameters

The secondary parameters of the study, evaluated at each study visit, are as follows:

- Surgical parameters of the AccuLIF cohort, including operative time, estimated blood loss and length of stay.
- The occurrence of neurologic complications, defined as abnormal changes from the pre-operative to post-operative neurologic evaluations.
- Changes in clinical outcomes, comparing pre- and post-operative patient measured outcomes defined as VAS, ODI and quality of life (QOL) as measured by SF-12.
- The occurrence and frequency of additional complications of the AccuLIF cohort, including infection and nonunion.
- Standard radiographic outcomes defined as; fusion status, cage placement, migration / subsidence and parameters of supplemental fixation hardware including screw placement and subsidence.

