#### **9.5 Efficacy Patient Population**

All patients enrolled in the study with any follow-up efficacy assessment (radiographic assessment) will be included in the efficacy patient population.

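### A 24-month CT fusion percentage on nonmissing data would describe mainly the subjects not shown fused at 12 months, not the cohort (minor)

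*Combined protocol and SAP*

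**What the plan says.** Section 9.1.4 lists "Standard radiographic outcomes defined as; fusion status, cage placement, migration / subsidence" among the secondary parameters, under a lead-in that has them assessed at every visit. The Evaluation Schedule labels its CT row as the fusion analysis.

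At 12 months the CT applies to all subjects; section 7.6 says "CT scan to assess bony fusion, will be taken as well". At 24 months it is selective. The schedule footnote reads "Month 24 CTs are only expected for subjects that did not have a successful fusion at Month 12", and section 7.7 agrees: "For subjects that did not have a successful fusion at Month 12, a 24 month CT scan will be taken to re-assess fusion". The footnote adds "All Month 24 CT collected will be analyzed", so a scan taken for another reason in a subject already fused also enters the analysis.

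The synopsis (Statistical Methodology) sets the base for categorical results: "Denominators for percentages will be the number of subjects in the respective patient population with nonmissing data". Section 9.5 defines the population broadly: "All patients enrolled in the study with any follow-up efficacy assessment (radiographic assessment) will be included in the efficacy patient population". Membership therefore does not depend on having a CT at any given visit.

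Section 9.3 bases the primary analyses on observed data and adds multiple imputation and last observation carried forward (LOCF) as sensitivity analyses. It does not mention fusion.

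**The concern.** Whether a subject has a 24-month CT depends on the 12-month CT result. A denominator of subjects with nonmissing data is then selected on the earlier value of the same outcome. Subjects already fused, the successes, drop out of the table unless they are scanned for some other reason.

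Section 16 plans a 2-year multi-center publication, and section 9.1.6 plans a comparison with published TLIF results. A 24-month figure from a subset enriched for nonunion could be read, or set beside the literature, as a cohort rate. Printing n/N would show that the base is small but not how it was selected. The figure would also move with the number of fused subjects who happened to be rescanned, which says nothing about the device.

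**Working it through.** The plan states no fusion rate, so there is no figure of its own to reproduce. The sample size in section 9.4.2 concerns lordosis and plays no part here, except that 100 enrolled with 20% dropout suggests about 80 evaluable subjects.

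**Inputs.** From the documents: N = 100 × 0.80 = 80. Assumed, for illustration only: 85% fused on CT at 12 months, and half of the rest fused by 24 months. Then:

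- fused at 12 months: 80 × 0.85 = 68
- not fused at 12 months: 80 − 68 = 12
- of these, fused by 24 months: 6

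**Cumulative fusion by 24 months**, counting 12-month fusions as standing: (68 + 6)/80 = 74/80 = 92.5% (exact 95% CI 84.4 to 97.2%).

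**Figure under the nonmissing-data rule.** If k fused subjects are also scanned and still fused, it is (6 + k)/(12 + k):

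| k | Percentage | 12-month nonunions as share of base |
|---|---|---|
| 0 | 6/12 = 50.0% (exact 95% CI 21.1 to 78.9%) | 100% |
| 12 | 18/24 = 75.0% | 50% |
| 34 | 40/46 = 87.0% | 26% |
| 68 | 74/80 = 92.5% | 15% |

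The two figures agree only when every fused subject is rescanned.

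**Other assumed rates.** Let p be the share fused at 12 months and c the share of the rest that convert. With no incidental scans the nonmissing-data figure is c, on 80(1 − p) subjects, and cumulative fusion is p + (1 − p)c. For p from 0.80 to 0.95 and c from 0.30 to 0.70:

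- nonmissing-data figure: 30 to 70%, on 16 down to 4 subjects
- cumulative fusion: 0.80 + 0.20 × 0.30 = 86% up to 0.95 + 0.05 × 0.70 = 98.5%

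The size depends on the assumptions, but the direction does not. With no incidental scans the gap is p(1 − c), which is positive whenever some subjects are fused at 12 months and some nonunions fail to convert.

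**What LOCF would give.** Applied to fusion, it would carry the 68 forward and return 74/80 = 92.5%. That would be a sensitivity result beside an observed-data table that still reads 6/12.

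**Nonunions without a 24-month CT.** Suppose 3 of the 12 have none and 5 of the other 9 convert. Conversion is 5/9 = 55.6% (exact 95% CI 21.2 to 86.3%). Keeping the 3 as not fused, cumulative fusion is (68 + 5)/80 = 73/80 = 91.25%. Dropping them gives 73/77 = 94.8%, which is biased upward: unscanned fused subjects stay in while unscanned nonunions leave.

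**The case against.** The strongest reply is that nothing commits the sponsor to a 24-month CT fusion percentage. The lead-in to section 9.1.4 also covers operative time, so it cannot be taken literally for every item. Section 16 names no fusion result. Rescanning only the unfused, to look at fusion again, fits a cumulative reading naturally, and a scan that was never expected need not count as missing. The denominator sentence stands in the synopsis and is not repeated in section 9.4.1. The case report forms, the image acquisition protocol and the formal SAP mentioned in section 9.1.6 are not available here and may settle the matter. Plain and flexion/extension films are taken in everyone at 24 months and could in principle support a fusion reading.

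Most of this stands, and it lowers the severity. It does not remove the gap: no available text exempts 24-month CT fusion from the nonmissing-data base, states the cumulative reading, or says that fusion is read from films.

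Three stronger readings are tempting and go too far.

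- A reader might infer that the plan has no carry-forward rule at all. Section 9.3 has LOCF, but only as a sensitivity analysis that neither names fusion nor changes the main table.
- A reader might infer that the scoring unit is undefined, since subjects are treated "at one or two contiguous levels between L2 and S1". The synopsis counts subjects, so percentages are per subject. What is open is whether a two-level subject must be fused at both levels.
- A reader might describe the 24-month set as nonunions only. The trigger is the absence of a successful fusion at 12 months, which may also take in subjects whose 12-month CT was missing or unevaluable.

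**Conclusion.** The point holds, as a minor one. Under the stated rules, the main observed-data table would give a 24-month CT fusion percentage for a group selected on 12-month status, plus any incidental scans. In the illustration this is 50% against 92.5% cumulatively. Every fusion, conversion and rescanning rate used is an assumption, and the consequence arises only if such a percentage is tabulated.

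Only a descriptive secondary outcome is affected. The primary lordosis analysis does not use CT fusion, and the 12-month CT rate is planned for the whole cohort. A reader might infer that the fusion results as a whole, or the trial's main conclusion, are compromised; the documents do not support that.

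**What to change.** In sections 9.1.4 and 9.1.5, or in the formal SAP, exempt 24-month CT fusion from the per-visit nonmissing-data denominator and specify:

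- **Conversion** among 12-month nonunions with a 24-month CT, as n/N.
- **Cumulative fusion by 24 months**, per subject, carrying 12-month CT fusions forward, over all subjects with an evaluable 12-month or 24-month CT. Keep 12-month nonunions without a 24-month CT in the denominator as not fused, and show their number. Label the figure as not routinely re-imaged once fused. Do not report a version that drops those nonunions.
- **24-month CTs in subjects already fused**, listed separately.
- **Classification rules**: how a missing or unevaluable 12-month CT is classed, and whether a two-level subject must be fused at both levels.

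The cost is some SAP and table-shell wording and a little table work, with no added imaging. The remaining weakness is that the cumulative rate assumes a 12-month CT fusion persists, which is why the label is needed.

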## 1 Introduction

This document is a protocol for a human research study. This study will be conducted in compliance with the protocol, Good Clinical Practice (GCP) Standards, associated Federal regulations and all applicable research requirements.

### 1.1 Background

An estimated 80% of the US population will experience some form of back pain in their lifetime. A number of treatment options are available to patients, based on age, presence of symptoms, and type of diagnosis. Chronic back pain associated with degenerative lumbar disease is a common symptom and tends to increase in severity with aging. In patients with prolonged, severe symptoms and/or instability, lumbar spondylotic disease, disc degeneration or herniation, facet degeneration, spondylolisthesis, stenosis, or scoliosis, lumbar fusion has been shown to be both clinically and cost effective. The objectives of fusion surgery of the lumbar spine include maintenance of coronal and sagittal balance, relief of pain, and solid arthrodesis. Several surgical approaches to interbody fusion have been developed such as anterior lumbar interbody fusion (ALIF), posterior lumbar interbody fusion (PLIF), lateral lumbar interbody fusion (LLIF) and transforaminal interbody fusion (TLIF). Each of these approaches has demonstrated high success rates, but each also comes with its own advantages and disadvantages.

Harms and Jezensky have been credited with development of the TLIF technique. The technique involves a partial facetectomy followed by unilateral discectomy and decortication of the endplates. An interbody implant packed with bone is inserted into the disc space via the transforaminal approach and tapped into place. The posterior disc space may also be packed with bone. Reported advantages of this technique include little retraction of the nerve root and thecal sac while yielding the benefits of circumferential fusion and maintaining or regaining lumbar lordosis. TLIFs can be performed through an open, less invasive or minimally invasive technique.

Advances in this technique have also been driven by innovations to spinal fusion implants and grafting options, which have led to improvements in the rates of successful fusions. Since Bagby invented the first cage device in 1988, numerous types of implants made from metal, carbon fiber composites, or titanium, have been designed and used in clinical cases. The implantation of interbody cages are imperative in the restoration of disc height and deformity correction in addition to restoring sagittal alignment. Recently, expandable interbody implants have been developed and introduced to the market. Features of this new technology include implants with short starting heights allowing surgeons to enter a collapsed disc space and then expanding the device in-situ, which could limit the impaction forces and overall destructive forces on the endplate. Although there is limited data on this novel technology, a few articles demonstrate that use of an expandable interbody fusion cage leads to good clinical results similar to static interbody cages such as achieving a solid bony fusion, improving a patient's quality of

CONFIDENTIAL

This material is the property of Stryker Spine. Do not disclose or use except as authorized in writing by Stryker.  
Page 14

life / pain assessment, and resulting in fewer mechanical device failures . Moreover, due to the dynamic technology of the expandable cages, some articles identify that greater improvements in vertebral disc space height and segmental lordosis can be achieved, all of which were accomplished without having to excessively drill, taper, or hammer instrumentation into the disc space in order to provide adequate distraction to access the vertebral space . Greater improvements in disc height and segmental lordosis have been identified as clinically important outcomes to pursue because the recovery and maintenance of these measures affects the load bearing on the surgical site after operation, functions of the paraspinal muscles, and energy consumption during gait . Moreover, restoration of lordosis has been noted as a significant factor when it comes to the occurrence of adjacent-level disease and symptomatic deformities, such as flat-back syndrome . Expandable interbody cages offer a unique solution to restoring sagittal alignment without compromising or sacrificing the integrity of the vertebral structures.

While several expandable technologies exist for interbody cages, many alternatives are still in the early stages of development and have not been thoroughly investigated to identify the benefits and/or harms associated with this technique and instrumentation. The purpose of this study is to fully evaluate the clinical and radiographic outcomes of the AccuLIF expandable TLIF cage as a means to achieving a solid arthrodesis and improved clinical outcomes while also restoring disc height, improving segmental lordosis, and maintaining sagittal balance.

## 1.2 Investigational Device

The AccuLIF System was designed to provide access and treatment to the lumbar spine via a transforaminal approach. The AccuLIF expandable lumbar interbody technology offers surgeon users the ability to insert an interbody device at a smaller starting height, place the device in the desired position within the disc space, and then expand the device to the desired height based on patient anatomy to ensure endplate-to-endplate fit. The small starting height of the implant is designed to help preserve endplate structural integrity, minimize impaction forces during insertion, help reduce nerve root retraction on insertion and during expansion, and help to reduce the potential for neural injury during insertion of the implant.

## 1.3 Pre-Clinical Data

Pre-clinical testing has been conducted in support of the AccuLIF system. The AccuLIF spacers have been tested according to ASTM and applicable standards. The AccuLIF spacers have been found to be substantially equivalent by US FDA via the 510(k) submission process.

## 1.4 Clinical Data to Date

This is the first, Stryker sponsored prospective clinical outcomes study of the AccuLIF System.

CONFIDENTIAL

This material is the property of Stryker Spine. Do not disclose or use except as authorized in writing by Stryker.  
Page 15

## 2 Study Objectives

### 2.1 Primary

The primary objective of this study to compare pre-operative and postoperative radiographic outcomes of a cohort treated for lumbar degenerative disease at one or two levels implanted with the AccuLIF spinal system at one level via TLIF procedure with supplemental fixation.

Primary Radiographic parameters are defined as:

- Disc height (anterior, middle, posterior in millimeters)
- Foraminal height (in millimeters)
- Segmental lordosis (at each TLIF level in degrees)
- Regional Lordosis: (inferior endplate T12-S1 in degrees)
- Sagittal balance: (C7-S1 in millimeters)
- Primary success is defined as an increase of 3 degrees or more of segmental lordosis post operatively.

It is hypothesized that patients implanted with the AccuLIF expandable TLIF cage will show restoration of anterior, middle, and posterior disc height, improve segmental lordosis and maintain regional and global sagittal balance post operatively.

Primary success is defined as an increase of 3 degrees or more of segmental lordosis post operatively.

It is also hypothesized that patients implanted with the AccuLIF expandable TLIF cage will show improvement in post-operative clinical outcomes when compared to pre-operative clinical status.

### 2.2 Secondary

The secondary objectives of the study are:

- To observe surgical parameters of the AccuLIF cohort.  
Defined as; operative time, estimated blood loss and length of stay.
- To assess the occurrence of neurologic complications by comparing pre-operative and postoperative neurologic evaluation.
- To assess clinical outcomes by comparing pre and post-operative patient measured outcomes defined as VAS, ODI and quality of life (QOL) as measured by SF-12 of the AccuLIF cohort.

CONFIDENTIAL

This material is the property of Stryker Spine. Do not disclose or use except as authorized in writing by Stryker.  
Page 16

- To observe the occurrence and frequency of additional complications of the AccuLIF cohort, including infection and nonunion.
- To observe standard radiographic outcomes defined as; fusion status, cage placement, migration / subsidence and parameters of supplemental fixation hardware including screw placement and subsidence.

## 2.3 Exploratory

The exploratory objectives of the study are:

- To evaluate the percentage of subjects that achieve  $> 3^\circ$  lordosis and no negative changes in regional lordosis and global sagittal balance
- To compare changes in disc height, lordosis, sagittal balance as categorized by disc morphology. Disc morphologies are defined as:
  - **Tall and lordotic** Average Disc Height  $\geq 11$  mm **AND** Disc Angle  $> 12^\circ$ .
  - **Moderate** Average Disc Height  $\geq 7$  mm to  $\leq 10$  mm **AND** Disc Angle  $\geq 5^\circ$  to  $\leq 12^\circ$ .
  - **Flat and compressed:** Average Disc Height  $0$  mm to  $\leq 6$  mm **AND** Disc Angle  $0^\circ$  to  $< 5^\circ$ .
- To compare summary AccuLIF data to published literature of comparable TLIF outcomes.

